10.3. Visit 5 – Follow-Up

A Follow-Up Visit will be conducted 7 to 11 days following Visit 4 or if a subject is discontinued prematurely. This visit will include the following assessments:

- Full PE (excluding breast, pelvic, rectal, and genitourinary exams); to include measurement of weight (no shoes, lightly clothed)
- Assessment of vital signs after a 5-minute seated rest
- Collection of venous blood for hematology and serum chemistry (see [Section 11.3.4](#) for complete listing of laboratory parameters)
- Urine pregnancy test for women of childbearing potential
- AE assessment
- Concomitant medications assessment

11. ASSESSMENTS

11.1. Pharmacodynamics

At Visits 2, 3, and 4 (Treatment Periods), samples will be drawn to measure plasma glucose levels. Venous blood samples will be drawn 10 ± 2 minutes before and immediately prior to dosing (-2 to 0 minutes), and then at 10, 20, 30, 40, 50, 60, 90, 120, 150, 180, 240, 300, and 360 minutes post-dosing (window allowance of ± 2 minutes).

Over the course of the study, approximately 15 blood samples (approximately 3 mL each) will be collected for each subject, for an approximate total volume of 45 mL per subject.

Plasma glucose levels will be used to calculate the following PD parameters: C_{max} , T_{max} , area over the curves (AOCs), and AUCs.

Detailed instructions for sample collection and preparation will be provided in a separate laboratory manual.

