11.2. Pharmacokinetics

At Visits 2, 3, and 4 (Treatment Periods), samples will be collected for determination of plasma insulin and pramlintide concentrations. Venous blood samples will be drawn 10 ± 2 minutes before and immediately prior to dosing (-2 to 0 minutes), and then at 10, 20, 30, 40, 50, 60, 90, 120, 150, 180, 240, 300, and 360 minutes post-dosing (window allowance of ± 2 minutes).

Over the course of the study, approximately 15 blood samples (approximately 4 mL each) will be collected for each subject, for an approximate total volume of 60 mL per subject.

Insulin and pramlintide concentrations will be used to calculate the following PK parameters: C_{max} , T_{max} , and AUC_{0-90} , AUC_{0-180} , AUC_{0-360} .

Detailed instructions for sample collection and preparation will be provided in a separate laboratory manual.

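### Sections 11.1 and 11.2 give one visit's blood volume as the whole-study total, so the stated PD and PK volumes are one third of what the schedule draws

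*Protocol*

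**What the plan says.** Section 11.1 places PD sampling at three visits: "At Visits 2, 3, and 4 (Treatment Periods), samples will be drawn to measure plasma glucose levels". It sets two pre-dose draws, "Venous blood samples will be drawn 10 ± 2 minutes before and immediately prior to dosing (-2 to 0 minutes", and then a post-dose series at "10, 20, 30, 40, 50, 60, 90, 120, 150, 180, 240, 300, and 360 minutes post-dosing". The next paragraph of the same section says "Over the course of the study, approximately 15 blood samples (approximately 3 mL each) will be collected for each subject". It puts the resulting PD volume at 45 mL.

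Section 11.2 has the same structure for PK: "At Visits 2, 3, and 4 (Treatment Periods), samples will be collected for determination of plasma insulin and pramlintide concentrations". The time points are the same, and the section then says "Over the course of the study, approximately 15 blood samples (approximately 4 mL each) will be collected for each subject". It puts the resulting PK volume at 60 mL.

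The same time points appear in the Synopsis, Table 2 (footnotes 8 and 9), Section 6.1 and Section 10.2.2. Table 2 marks PK and PD collection at Visits 2, 3 and 4, and Section 10.2.2 has the treatment visit procedures repeated after each washout.

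**The concern.** The sampling paragraph and the volume paragraph of each section cannot both be right. Fifteen is the number of time points in one visit, yet it is given as the number of samples for the whole study.

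The figure describes what is taken from each subject. Under Section 16.2 the IRB must review and approve the protocol before enrolment, and under Section 16.3 subjects must be told the possible risks. A reader who takes the stated totals at face value would believe that one third of the scheduled volume is drawn.

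Timing adds some weight. With two washouts of 7 to 11 days, the three sampling days fall within 14 to 22 days on the planned schedule. Follow-up hematology comes after all of them, so a correct volume also helps in reading any change in hemoglobin from Screening. Section 7.3 excludes low hemoglobin or hematocrit and blood donation within 8 weeks before Screening. The protocol gives no reason for these exclusions, so a link to study blood volume is inference.

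**Working it through.** **Inputs**
- Pre-dose draws per visit: 2 (Sections 11.1 and 11.2).
- Post-dose draws per visit: 13 (10, 20, 30, 40, 50, 60, 90, 120, 150, 180, 240, 300 and 360 minutes; same sections).
- Visits with sampling: 3 (Visits 2, 3 and 4; same sections and Table 2).
- Volume per sample: about 3 mL for PD (Section 11.1) and about 4 mL for PK (Section 11.2).

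**Formula**

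Volume = draws per visit × mL per sample × number of visits, with draws per visit = 2 + 13 = 15.

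**Reproducing the plan's figures**

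With one visit:
- PD: 15 × 3 mL = 45 mL, as stated.
- PK: 15 × 4 mL = 60 mL, as stated.

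Both match exactly, so the multiplication is sound but covers one visit only.

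**Whole study**

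| | Samples | Scheduled volume | Stated volume |
|---|---|---|---|
| PD | 15 × 3 visits = 45 | 45 × 3 mL = 135 mL | 45 mL |
| PK | 15 × 3 visits = 45 | 45 × 4 mL = 180 mL | 60 mL |
| Sum (derived here) | | 315 mL | 105 mL |

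Stated over scheduled: 105 / 315 = 1/3. Difference: 315 − 105 = 210 mL per subject.

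**Other readings tried**
- Two visits only: 30 × 3 = 90 mL PD and 30 × 4 = 120 mL PK. No match.
- One pre-dose draw instead of two: 14 × 3 × 3 = 126 mL PD and 14 × 3 × 4 = 168 mL PK. No match.
- One tube serving both assays: 45 × 3 = 135 mL to 45 × 4 = 180 mL in all, still above 105 mL.
- Fifteen samples over three visits would need 5 time points per visit; the schedule has 15.

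No reading of the schedule gives 45 mL and 60 mL over three visits.

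**Interval**

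Visit 2 to Visit 4 spans two washouts: 7 + 7 = 14 days to 11 + 11 = 22 days.

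**The case against.** The strongest reply is that this is a labelling slip with no operational effect. The sampling schedule is clear and consistent wherever it appears, so sites would draw the same tubes either way. No endpoint, PK or PD parameter, dose, eligibility decision or analysis uses the volume sentence. The IRB receives the full protocol, with the visit-by-visit schedule directly above the wrong sentence. All of this stands, and it limits the consequence to the stated subject burden.

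Three further points also stand:
- The consent form is not available for this review and may give the volume correctly, so it cannot be said that subjects were given the wrong figure.
- The protocol sets no blood volume limit, and nothing here shows that 315 mL would be harmful.
- The protocol never adds PD and PK. The 315 mL sum assumes separate tubes, the natural reading of separate volumes, but collection details are left to a laboratory manual.

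None of this rescues the stated totals. The hedge in the wording cannot absorb a factor of three, and each volume is wrong on its own without any adding of PD and PK.

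**Conclusion.** The concern holds. The whole-study totals in Sections 11.1 and 11.2 are wrong as written: each is one third of what the same section schedules (PD 45 mL against 135 mL, PK 60 mL against 180 mL). These results assume that a subject completes all three periods and that the stated volumes per sample are right. The combined understatement of 210 mL also assumes separate PD and PK tubes. Screening and follow-up safety blood lies outside these figures and would add to them; the protocol gives no volumes for it.

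The error lies in the account of subject burden, not in the statistics. It should be corrected because the number is understated threefold in an operative section that goes to the IRB.

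**What to change.** In Section 11.1, state about 15 samples of about 3 mL at each treatment visit (about 45 mL per visit), making about 45 samples and 135 mL per subject over the three visits. In Section 11.2, state about 15 samples of about 4 mL at each treatment visit (about 60 mL per visit), making about 45 samples and 180 mL per subject.

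It would help to add the combined PK and PD total, about 315 mL if tubes are separate, with the safety laboratory volume given alongside it. If the consent form or any IRB document carries the 45 mL or 60 mL figure as a study total, correct it there as well.

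The cost is two corrected sentences and, where the figure was reused, a consent update. The sampling schedule and the analysis do not change. The stated burden becomes less favourable.

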11.2. Pharmacokinetics

At Visits 2, 3, and 4 (Treatment Periods), samples will be collected for determination of plasma insulin and pramlintide concentrations. Venous blood samples will be drawn 10 ± 2 minutes before and immediately prior to dosing (-2 to 0 minutes), and then at 10, 20, 30, 40, 50, 60, 90, 120, 150, 180, 240, 300, and 360 minutes post-dosing (window allowance of ± 2 minutes).

Over the course of the study, approximately 15 blood samples (approximately 4 mL each) will be collected for each subject, for an approximate total volume of 60 mL per subject.

Insulin and pramlintide concentrations will be used to calculate the following PK parameters: C_{max} , T_{max} , and AUC_{0-90} , AUC_{0-180} , AUC_{0-360} .

Detailed instructions for sample collection and preparation will be provided in a separate laboratory manual.

11.3. Safety Parameters

11.3.1. Vital Sign Measurements

Vital signs, including measurements of temperature ($^{\circ}\text{C}$), respiration (breathes per minute), HR (beats per minute), and BP (mmHg) will be measured (after 5 minutes seated rest) at the times specified in the Schedule of Assessments. Additional or changes to collection times, or collection using automated devices is permitted, as necessary, to ensure appropriate subject's safety.

Vital signs will be measured according to standard of practice of the site and recorded in the eCRF.

11.3.2. Physical Examination

Full PEs will be performed at Screening and Follow-Up Visits. The PE will include a review of all body systems (excluding breast, pelvic, rectal, and genitourinary) and include measurements

of weight (in kg) and height (in cm; height to be measured only at Screening Visit). Symptom-directed PEs are to be performed at Visits 2, 3, and 4.

Findings at Screening are to be recorded as medical history. Any abnormal or clinically significant findings from the PE must be recorded in the AE eCRF.

11.3.3. Electrocardiogram (12-Lead ECG)

Single, supine 12-lead ECGs should be obtained at Screening per the site's standard practice and before assessment of BP and HR, and prior to blood collections.

11.3.4. Laboratory Assessments

The tests outlined in [Table 6](#) will be performed at the specified time points described in the Schedule of Assessments.

Table 6: Clinical and Safety Related Laboratory Tests

Hematology	Chemistry	Urine	Laboratory
Hematocrit	Albumin	β-hCG	C-peptide
Hemoglobin	Alkaline phosphatase	Drug screen	HbA1c
Platelet count	ALT		Pramlintide
RBC count	AST		Insulin
WBC count	Calcium Creatinine Glucose Potassium Sodium Triglycerides		

The site's laboratory will be used for safety lab analysis. A procedures manual will be provided to each site by the central laboratory. This manual will cover procedures for the collection, processing, and shipping of blood samples, along with the Clinical Laboratory Improvement Act (CLIA) certification and normal ranges for the central laboratory.

The laboratory will provide sites with all supplies needed for collection, processing, and shipping of all blood samples, as well as point-of-care urine pregnancy tests.

11.3.4.1. Drug Screen

A urine drug screening is to be performed at Screening and include cocaine, THC, opiates, amphetamines, methamphetamine, and phencyclidine. Investigator will exercise discretion in allowing or excluding a subject from study participation based on a positive test for one of these additional analytes.

At the investigator's discretion, subjects with a positive result for drugs other than THC (which is allowed at the investigator's discretion) will be allowed to participate if the subject reports use

of a concomitant medication that explains the result (eg, positive urine test for opiates in a subject reporting use of cough syrup containing dextromethorphan).

11.3.4.2. Pregnancy Screen

Female participants of childbearing potential require a negative urine pregnancy test at Screening and Visits 2 through 5.

11.3.5. Local Tolerability

Local tolerability will be assessed at Visits 2, 3, and 4 as follows:

- The investigator will use the modified Draize scale ([Appendix 1](#)) to assess erythema and edema formation at the injection site at 30, 90, and 360 minutes (\pm 2 minutes) after injection of study drug(s). If any scores remain > 1 at the 360-minute evaluation, the subject may leave the clinic but will be instructed to contact a study staff member if the condition fails to resolve. Every effort should be made to ensure that the same investigator will assess the injection sites on the subject at each visit.
- Subjects will complete a 11-point Numeric Rating Scale (NRS) questionnaire regarding injection site discomfort 10 and 30 minutes (\pm 2 minutes) after injection of study drug ([Appendix 2](#)). Question Q1c is to be answered at 360 mins post-study drug injection.

12. SAFETY AND ADVERSE EVENT (AE) REPORTING

12.1. Definition of an Adverse Event

An AE is any untoward medical occurrence in a clinical investigation subject administered a pharmaceutical product and which is not necessarily required to have a causal relationship with this treatment. An AE can therefore be any unfavorable and unintended sign, symptom, or disease temporally associated with the use of a medicinal product, whether considered related to the medicinal product. Examples of AEs include:

- Abnormal test findings
- Clinically significant symptoms and signs
- Changes in PE findings which are untoward and deemed clinically significant by the investigator
- Allergy/hypersensitivity

The criteria for determining whether an abnormal objective test finding may be reported as an AE are as follows:

- Test result is associated with accompanying symptoms
- Test result requires additional diagnostic testing or medical/surgical intervention
- Test result leads to a change in study dosing or discontinuation from the study
- significant additional concomitant drug treatment or other treatment
- Test result is considered to be an AE by the investigator or sponsor

Repeat of a test based on an abnormal result in the absence of the above conditions does not constitute an AE. Any abnormal test result determined to be an error does not require reporting as an AE.

A treatment-emergent AE (TEAE) is an AE that either commenced following initiation of study treatment or was present prior to study treatment but increased in frequency or severity following initiation of study treatment.

Standard medical terminology should be used in describing AEs. Informal descriptions should be avoided.

12.1.1. Adverse Events of Special Interest

An adverse event of special interest (AESI) (serious or non-serious) is one of scientific and medical concern specific to the sponsor's product or program, for which ongoing monitoring and rapid communication by the investigator to the sponsor could be appropriate. Such an event might require further investigation in order to characterize and understand it (ICH E2F, 2008). AESIs for PRAM9 are as follows: hypoglycemia, nausea, and vomiting.

12.2. Reporting Adverse Events

All observed or volunteered AEs regardless of treatment group or suspected causal relationship to the study treatment will be reported with 2 exceptions. Injection site reactions will not be considered an AE unless a skin reaction or pain requires medical intervention.

For all AEs, the investigator must pursue and attempt to obtain information adequate to determine the outcome of the AE and to assess whether it meets the FDA criteria for classification as an SAE, requiring immediate notification to Xeris Pharmaceuticals.

For all AEs, follow-up by the investigator is required until the event resolves or stabilizes at a level acceptable to the investigator to consider it resolved. For unresolved AEs to be considered stable, the Xeris Medical Monitor must concur with that assessment.

As part of ongoing safety reviews conducted by the sponsor, any nonserious AE that is determined to be serious (according to the FDA definitions of an SAE) will be reported by the sponsor as an SAE. To assist in the determination of case seriousness, further information may be requested from the investigator to provide clarity and understanding of the event in the context of the clinical study.

12.3. Reporting Period

For all AEs, the reporting period to Xeris Pharmaceuticals begins from the subject providing informed consent, through the Follow-Up Visit. All AEs will be followed until resolution or the subject is medically stable.

12.4. Serious Adverse Events

An SAE is any untoward medical occurrence at any dose which:

- Results in death
- Is life-threatening
- Requires inpatient hospitalization or prolongation of existing hospitalization
- Results in persistent or significant disability/incapacity
- Is a congenital anomaly/birth defect
- Is an important medical event (IME)

Medical and scientific judgment should be exercised in determining whether expedited reporting is appropriate in other situations, such an IME that may not be immediately life-threatening or result in death or hospitalization but may jeopardize the subject or may require intervention to prevent one of the other outcomes listed in the definition above. These events should also usually be considered serious. Examples of such events are intensive treatment in an emergency room or at home for allergic bronchospasm or blood dyscrasias or convulsions which do not result in hospitalization.

12.5. Severity Assessment

On the AE eCRF, the investigator will use the adjectives “mild,” “moderate,” or “severe” to describe the maximum intensity of the AE. These intensity grades are defined as follows in [Table 7](#), which follows.

Table 7: Adverse Event Severity Assessment

Mild	Does not interfere with subject’s usual function
Moderate	Interferes to some extent (< 50%) with subject’s usual function
Severe	Interferes significantly ($\geq 50\%$) with subject’s usual function

The terms “serious” and “severe” are not synonymous. The term “severe” is often used to describe the intensity (severity) of a specific event. The event itself, however, may be of relatively minor medical significance. This is not the same as “serious,” which is based on subject/event outcome or action criteria. Accordingly, a severe event is not necessarily a serious event.

12.6. Causality Assessment

The investigator will use the following question when assessing causality of an AE to the study drug, where an affirmative answer designates the event as a suspected adverse reaction: “Is there a reasonable possibility that the drug caused the event?” A “reasonable possibility” means that there is evidence to suggest a causal relationship between the drug and the AE. The investigator’s assessment of causality must be provided for all AEs (related or unrelated). The investigator must record the causal relationship in the eCRF, as appropriate, and report such an assessment in accordance with the SAE reporting requirements, if applicable ([Section 12.9](#)). All investigator assessments of AEs must be documented in the source documentation.

12.7. Withdrawal Due to Adverse Events

Withdrawal due to AE should be distinguished from withdrawal due to insufficient response and recorded on the appropriate eCRF. When a subject withdraws due to an SAE, the SAE must be reported in accordance with the reporting requirements (see [Section 12.9](#)).

12.8. Eliciting Adverse Event Information and Reporting

The investigator is to report all directly observed AEs and all AEs spontaneously reported by the study subject. Each study subject will be questioned about AEs. Each AE is to be assessed to determine if it meets the criteria for SAEs. If an SAE occurs, expedited reporting will follow the provisions of [Section 12.9](#).

12.9. Serious Adverse Event Reporting Requirements

If an SAE occurs, Xeris Pharmaceuticals is to be notified within 24 hours of awareness of the event by the investigator. If the SAE is fatal or life-threatening, notification to Xeris

Pharmaceuticals must be made immediately, irrespective of the extent of available AE information. This time frame also applies to follow-up on previously forwarded SAE reports.

In the rare event that the investigator does not become aware of the occurrence of an SAE immediately (eg, a study subject initially seeks treatment elsewhere), the investigator is to report the event within 24 hours after learning of the event and document the time of first awareness of the AE.

A death occurring during the study, during the study follow-up period, or within 14 days after stopping treatment with test drug must be reported to Xeris Pharmaceuticals or its designee(s) immediately, whether it is considered treatment-related. Initial SAE reports must be followed by detailed descriptions. These should include copies of hospital case records and other documents when requested. Telephone and email reports must be confirmed promptly either by facsimile or by overnight courier or mail.

Under 21 CFR 312.32(c), Xeris Pharmaceuticals or its designee(s) is required to notify FDA and all participating investigators in an IND safety report (ie, 7- or 15-day expedited report) of potentially serious risks from clinical trials or any other source as soon as possible, but no later than 15 calendar days after the safety information is received and a determination is made that the information qualifies for reporting.

12.10. Nonserious Adverse Event Reporting Requirements

All AEs will be reported on the AE page(s) of the eCRF. AEs should be reported using concise medical terminology on the eCRFs as well as on the form for collection of the SAE information.

12.11. AE Reporting Requirements to Regulatory Authorities

AE reporting by the sponsor, including suspected serious unexpected adverse reactions, will be carried out in accordance with applicable regulations.

The investigator must notify the IRB/Independent Ethics Committee (IEC) of the occurrence of any SAE, in writing, as soon as is practicable and in accordance with local regulations. A copy of this notification must be provided to Xeris Pharmaceuticals or its designee.

In the event of an SAE that meets the criteria for expedited reporting, an SAE report will be prepared for submission to the FDA and any other applicable authorities by Xeris Pharmaceuticals or its designee.

12.12. Pregnancy

The active pharmaceutical products in Xeris Pharmaceuticals' PRAM9 pramlintide-insulin are in Pregnancy Category B. Female subjects of childbearing potential will be tested (urine) for pregnancy at the Screening Visit. A woman is considered to be of childbearing potential if she is post menarcheal, has not reached a postmenopausal state (≥ 12 continuous months of amenorrhea with no identified cause other than menopause), and has not undergone surgical sterilization (removal of ovaries and/or uterus).

Any subject found to be pregnant at the Screening Visit (Visit 1) will not be randomized to a treatment sequence. Any subject who is found to be pregnant at one of the treatment visits will be withdrawn from the study immediately and no further study treatments will be given.

Pregnancy at the Follow-Up Visit will be noted, but the visit will be completed. Any pregnancy in a subject who received at least one dose of study drug will be followed until resolution (ie, birth or voluntary or spontaneous termination of the pregnancy). Any pregnancy outcome that meets the criteria for an SAE will be reported as an SAE.

